10.3 Analysis Sets

For the purposes of analysis, the following analysis sets will be used for each sub-protocol in this trial:

Table 10.3-1: Palmoplantar Psoriasis Sub-Protocol Analysis Sets

Population	Description
Enrolled	All participants who sign informed consent.
Randomized (Full Analysis Set [FAS])	All participants who were randomized to any treatment arm in the study.
Safety	All randomized participants who take at least 1 dose of study intervention. Participants will be analyzed according to intervention received.
Defined Analysis Data Sets	Description
Analysis set for primary estimand of pp-PASI-75	All randomized participants; all available data up to Week 16 database lock. Participants who discontinued prior to Week 16 will be imputed as non-responders in the analysis dataset. Following the intent-to-treat principle, participants will be analyzed according to the intervention group assigned at randomization.
Analysis set for secondary estimand of pp-PGA 0/1	All randomized participants; all available data up to Week 16 database lock. Participants who discontinued prior to Week 16 will be imputed as non-responders in the analysis dataset. Following the intent-to-treat principle, participants will be analyzed according to the intervention group assigned at randomization.
Analysis set for safety	All safety events reported for all randomized participants who are exposed to study intervention. For participants who discontinue study intervention all post discontinuation up to Day 28 post last dose of study intervention will be included in the safety summaries. Participants will be analyzed according to intervention received.

Abbreviations: pp-PASI, palmoplantar Psoriasis Area and Severity Index; pp-PGA, palmoplantar physician global assessment.

Table 10.3-2: Genital Psoriasis Sub-Protocol Analysis Sets

Population	Description
Enrolled	All participants who sign informed consent.
Randomized (Full Analysis Set [FAS])	All participants who were randomized to any treatment arm in the study.
Safety	All randomized participants who take at least 1 dose of study intervention. Participants will be included in the treatment group to which they were randomized.
Defined Analysis Data Sets	Description
Analysis set for primary estimand of s-PGA-G 0/1	All randomized participants; all available data up to Week 16 database lock. Participants who discontinued prior to Week 16 will be imputed as non-responders in the analysis dataset. Following the intent-to-treat principle, participants will be analyzed according to the intervention group assigned at randomization.
Analysis set for secondary estimand of GenPs itch NRS	All randomized participants; all available data up to Week 16 database lock. Participants who discontinued prior to Week 16 will be imputed using multiple imputation in the analysis dataset. Following the intent-to-treat principle, participants will be analyzed according to the intervention group assigned at randomization.
Analysis set for safety	All safety events reported for all randomized participants who are exposed to study intervention. For participants who discontinue study intervention all post discontinuation up to Day 28 post last dose of study intervention will be included in the safety summaries. Participants will be analyzed according to intervention received.

Abbreviations: GenPs, genital psoriasis; NRS, numerical rating scale; s-PGA-G, static Physician's Global Assessment of Genitalia.

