12-lead ECG	X	12-lead ECGs should be recorded after the participant has been supine for at least 5 minutes. A single ECG should be collected. See Section 9.4.3 .

Table 2-1: Non-pustular Palmoplantar Psoriasis Sub-protocol Screening Procedural Outline (IM011112)

Procedure	Screening Visit (Day -28 to Day -1)	Notes
Adverse Event Reporting		
Monitor for AE and SAE Assessment	X	All AEs and SAEs must be collected from the date of participant's written consent until 30 days post discontinuation of dosing or participant's participation in the study if the last scheduled visit occurs at a later time.
Clinical Efficacy		
pp-PGA	X	Non-pustular PP plaque psoriasis. Participants with PP pustulosis or PP pustular psoriasis are not eligible for enrollment. Refer to Section 6 for detailed eligibility criteria.
pp-PASI	X	Refer to Section 6 for detailed eligibility criteria.
Number of Pustules Present	X	Participants with a total maximum of 5 sterile pustules across both palms and soles and limited only to psoriatic plaques will be eligible for enrollment. The total number and location of pustules must be documented if present.
s-PGA	X	Refer to Section 6 for detailed eligibility criteria.
Evidence of Typical Plaque Psoriasis Outside Palms and Soles	X	Refer to Section 6 for detailed eligibility criteria.
Dispense E-diary	X	All consented participants will be given a diary device at the screening visit and will begin recording PP psoriasis symptoms on a daily basis in the diary device. Participants who are not randomized will stop recording and return

Table 2-1: Non-pustular Palmoplantar Psoriasis Sub-protocol Screening Procedural Outline (IM0111112)

Procedure	Screening Visit (Day -28 to Day -1)	Notes
		their diary device to the site. Participants who are randomized will continue recording their psoriasis symptoms on a daily basis in the diary device through Week 16 and for 7 days prior to each subsequent visit through Week 52.

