9.2 Adverse Events

The definitions of an AE or SAE can be found in [Appendix 3](#).

AEs will be reported by the participant (or, when appropriate, by a caregiver, a surrogate, or the participant's legally acceptable representative).

The investigator and any qualified designees are responsible for detecting, documenting, and reporting events that meet the definition of an AE or SAE and remain responsible for following up on AEs that are serious, considered related to the study intervention or the study, or that caused the participant to discontinue before completing the study.

Refer to Appendix 3 for SAE reporting.

9.2.1 *Period and Frequency for Collecting AE and SAE Information*

All AEs and SAEs must be collected from the time of signing the consent, including those thought to be associated with protocol-specified procedures and until 30 days following discontinuation of dosing or participant's participation in the study if the last scheduled visit occurs at a later time.

The investigator must report any SAE that occurs after these periods and that is believed to be related to a study intervention or protocol-specified procedure.

- All SAEs will be recorded and reported to the Sponsor or designee, promptly and not to exceed 24 hours of awareness of the event, as indicated in Appendix 3.
- The investigator will submit any updated SAE data to the Sponsor or designee within 24 hours of updated information being available.

Investigators are not obligated to actively seek AEs or SAEs in former study participants. However, if the investigator learns of any SAE, including a death, at any time after a participant has been discharged from the study, and he/she considers the event reasonably related to the study intervention or study participation, the investigator must promptly notify the Sponsor.

The method of evaluating and assessing causality of AEs and SAEs and the procedures for completing and reporting/transmitting SAE reports are provided in Appendix 3.

9.2.2 *Method of Detecting AEs and SAEs*

AEs can be spontaneously reported or elicited during open-ended questioning, examination, or evaluation of a participant. Care should be taken not to introduce bias when collecting AEs and/or SAEs. Inquiry about specific AEs should be guided by clinical judgment in the context of known AEs, when appropriate for the program or protocol.

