10.4.5 Safety Analyses

Safety data will be analyzed for AEs, SAEs, laboratory analytes, vital signs. Safety will be summarized using the as-treated population for each sub-protocol. Categorical data will be summarized as frequency counts and percentages. Continuous data will be summarized using n, mean, SD, median, minimum, and maximum unless otherwise specified. Safety will be analyzed through Week 16 and then up to end of study.

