10.5 Interim Analyses

No interim is currently planned.

Week 16 Primary Analysis

A 16-week primary analysis will occur once all randomized participants have completed through Week 16 or have discontinued prior to Week 16 in each sub-protocol independently. Analyses of the collected efficacy and safety data will be performed independently also. The study participants and investigators will remain blinded to the initial treatment assignment received from Day 1 to Week 16 and the results of this analysis throughout the study. The Sponsor and site-facing study team will be unblinded to the individual treatment assignments following the last Week 16 visit.

Additional details of these analyses will be described in the SAP. A final analysis will be performed after all participants complete the Week 52 visit or discontinue prior to the Week 52 visit.

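### For participants who stop treatment early, the safety tables are defined to end at Day 28 although adverse events are collected for longer, and the Week 52 final-analysis trigger does not fit a safety scope that runs to Week 56

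*Combined protocol and SAP*

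**What the plan says.** **Collection.** Section 9.2.1 requires all AEs and SAEs to be collected from consent "until 30 days following discontinuation of dosing or participant's participation in the study if the last scheduled visit occurs at a later time". The Schedule of Activities repeats this rule in both sub-protocols. The footnotes to Tables 2-3 and 2-6 place the safety follow-up visit 28±3 days after the last dose. Section 8.1.2 says that participants who stop study intervention are still to be followed for outcome data until the study concludes.

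**Analysis set.** The safety row is the same in Tables 10.3-1 (palmoplantar) and 10.3-2 (genital). It opens broadly: "All safety events reported for all randomized participants who are exposed to study intervention". The next sentence concerns only participants who discontinue study intervention, and says that for them "all post discontinuation up to Day 28 post last dose of study intervention will be included in the safety summaries".

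**Timing of the final analysis.** Section 10.4.5: "Safety will be analyzed through Week 16 and then up to end of study". Section 5.3 defines end of study as the last participant's last visit. In Tables 2-3 and 2-6 the last scheduled visit is Week 56 (D393). Section 10.5: "A final analysis will be performed after all participants complete the Week 52 visit or discontinue prior to the Week 52 visit".

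**The concern.** The collection rule and the analysis rule use different windows, and nothing says how an event that lies between them is reported. An event recorded at a follow-up visit held within its permitted window, on Day 29, 30 or 31, is collected data with no place in the stated summaries. An event recorded later, in someone who stopped treatment but stayed in the study, is in the same position.

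This bears on a listed objective. Both sub-protocols have a secondary safety endpoint covering Week 0 to Week 16 (Tables 4-1 and 4-2). A participant who stops early and remains in follow-up can have events inside that period but more than 28 days after the last dose.

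The second problem is one of timing. A participant who has just attended Week 52, or who discontinued shortly before it, satisfies the Section 10.5 condition before the off-drug follow-up is complete. A team that ran the analysis as soon as the condition was met would produce safety tables that do not reach the end of study required by Section 10.4.5. Two analysts following this text could reasonably build different safety tables.

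**Working it through.** The plan gives no figure for this gap, so there is none to reproduce. The check is day arithmetic.

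**Inputs from the document**
- Collection: 30 days after last dose, or end of participation if later (Sections 2 and 9.2.1).
- Summary window for discontinuers: 28 days after last dose (Tables 10.3-1 and 10.3-2).
- Follow-up visit: 28±3 days after last dose (Tables 2-3 and 2-6).
- Visit days: Week 16 = D113, Week 52 = D365, Week 56 = D393 (Tables 2-2, 2-3, 2-5 and 2-6).

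**1. Minimum gap**
- Collection minus summary: 30 − 28 = 2 days.
- The visit window runs from 28 − 3 = Day 25 to 28 + 3 = Day 31. If the visit is on Day 31, the gap is 31 − 28 = 3 days.

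**2. Gap for discontinuers who stay in follow-up**

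Days outside the summaries = end day − stopping day − 28, with zero as the floor. The stopping days are assumed, and the last column also assumes follow-up to D393.

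| Last dose (assumed) | Uncovered days before Week 16 (D113) | Uncovered days before Week 56 (D393) |
|---|---|---|
| D29 | 113 − 29 − 28 = 56 | 393 − 29 − 28 = 336 |
| D57 | 113 − 57 − 28 = 28 | 393 − 57 − 28 = 308 |
| D85 | 113 − 85 − 28 = 0 | 393 − 85 − 28 = 280 |
| D225 | not applicable | 393 − 225 − 28 = 140 |
| D281 | not applicable | 393 − 281 − 28 = 84 |

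The Week 0 to 16 comparison is therefore affected only by stops before D85 in participants who remain in follow-up.

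**3. Final-analysis trigger**
- Week 56 minus Week 52: 393 − 365 = 28 days.
- The document gives no accrual period. Assume uniform accrual over 9, 12 or 18 months (39, 52 or 78 weeks), no dropout, and a data cut on the day of the last Week 52 visit. The share of participants whose 4-week follow-up is incomplete at that cut is then:
  - 4/39 = 10.3%
  - 4/52 = 7.7%
  - 4/78 = 5.1%
- Most of these participants would have part of their follow-up, not none.

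**The case against.** The strongest reply is that this is a difference of wording with little consequence.

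- **The row opens with all safety events in exposed participants.** The Day 28 sentence names only those who discontinue. A reader might infer that every participant's safety data are cut at Day 28. The text does not support that, because completers are not expressly truncated. This objection stands and limits the point to discontinuers.
- **Section 10.5 sets an earliest condition, not a data cut-off.** A final analysis run after the last Week 56 visit would satisfy Sections 10.5, 10.4.5 and 5.3 together. A reader might infer that the plan discards the Week 52 to 56 data, but no sentence says so. This also stands: the trigger permits an early analysis and does not require one.
- **A shorter summary window may be deliberate.** Day 28 matches the nominal follow-up visit, and Section 9.3 puts five half-lives at about 3 days, so Days 29 to 31 are well beyond expected exposure. That could justify an on-treatment summary. The document does not give this reason, however, and does not say where the later collected events are reported.
- **The detail is left to the SAP** (Sections 10.4 and 10.5). The supplied text contains no further SAP detail on this point, so it cannot be checked. The deferral does not itself reconcile the conflicting sections.
- **Safety surveillance does not depend on the tables.** SAEs go to the sponsor within 24 hours (Section 9.2.1). True, but the point is about the completeness of the reported summaries.

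**Conclusion.** The point holds in a limited form. For participants who discontinue study intervention, in both sub-protocols, the stated safety summaries end before collection does. The gap is at least 2 days, or 3 if the follow-up visit falls on Day 31. It is longer for those who remain under observation: for example, 56 days of the placebo-controlled period for an assumed stop at D29. The longer figures depend on discontinuers actually staying in follow-up as Section 8.1.2 requires.

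The Week 52 trigger is inconsistent with the end-of-study safety scope by 28 days. The 5% to 10% of participants with incomplete follow-up is only illustrative. It rests on the assumed accrual periods and on a cut on the day of the last Week 52 visit, neither of which the document states.

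Two further inferences should be resisted. The ratio 2/30 (6.7%) is a share of calendar days and says nothing about the share of events missed, since no event rate is given. Nor does the document say that early stoppers stop mainly because of adverse events. Section 8.1 lists several reasons without frequencies.

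The consequence is incomplete or irreproducible safety tables. The Week 16 efficacy analyses are not touched. The point is modest but worth correcting, because the sections conflict and the correction costs little.

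**What to change.** 1. In the safety rows of Tables 10.3-1 and 10.3-2, align the window with Section 9.2.1 in full: 30 days after the last dose or the end of participation, whichever is later. Extending it only to 30 days or to the follow-up visit would leave a mismatch for discontinuers who stay in the study. If an exposure-related summary is wanted, flag or tabulate separately the events that occur more than 30 days off drug.
2. In Section 10.5, tie the final safety analysis and database lock to the last participant's Week 56 or safety follow-up visit, or study withdrawal, so that it agrees with Sections 10.4.5 and 5.3.
3. Carry the same definitions into the SAP, which Section 10.4 says will be finalised before the Week 16 lock.

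The cost is wording, plus a final lock about 4 weeks later than the Week 52 trigger would allow. Data collection need not change.

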10.4 Statistical Analyses

The statistical analysis plan (SAP) will be developed and finalized before database lock at week 16 and will describe the selection of participants to be included in the analyses and procedures for accounting for missing, unused, and spurious data for each sub-protocol. Below is a summary of planned statistical analyses of the primary and secondary endpoints.

A description of the participant population will be included in the clinical study report (CSR), including subgroups of age, gender, race, and other study-specific populations and demographic characteristics. A description of participant disposition will also be included in the CSR.

Participant characteristics and/or demographic data may be pooled across studies for future analysis.

10.4.1 General Considerations

Efficacy Analyses

Descriptive statistics will be presented by the treatment group. Categorical data will be summarized as frequency counts and percentages. Continuous data will be summarized using n, mean, standard deviation (SD), median, minimum, and maximum unless otherwise specified. Efficacy values will be summarized for all visits in which the variable is assessed. Details of the planned analyses of endpoints during the 16-week double-blinded placebo-controlled period will be documented in the SAP and finalized before the primary analysis database lock for each sub-protocol.

During the first 16 weeks of treatment, data will be presented for the following treatments for each sub-protocol:

- deucravacitinib 6 mg QD
- placebo

After Week 16, data for each sub-protocol will be presented for the following treatments:

- deucravacitinib 6 mg QD
- placebo → deucravacitinib 6 mg QD (starting at Weeks 16 through 52)

The main estimands for the primary and key secondary objectives are summarized below in [Table 10.4.1-1](#) for non-pustular PP psoriasis and in [Table 10.4.1-2](#) for GenPs, respectively.

Table 10.4.1-1: Summary of the Attributes of the Main Estimand for the Primary and Key Secondary Objectives of Palmoplantar Psoriasis Sub-protocol

Primary Objective			
Estimand Attribute	Definition		
Treatment	Deucravacitinib 6 mg QD versus Placebo		
Population	Participants with moderate-to-severe non-pustular palmoplantar psoriasis		
Variable	pp-PASI-75: Individual patient’s binary outcome (Yes or No) of achieving 75% improvement at Week 16 in pp-PASI score from baseline.		
Intercurrent Events (ICEs)	Event	Strategy	Description
	Discontinuation of intervention and study early prior to Week 16 assessment	Composite variable	Participant will be counted as a non-responder
	Lost to follow-up prior to Week 16 or otherwise missed assessment at Week 16	Composite variable	Participant will be counted as a non-responder
Population-level Summary	Odds ratio of achieving 75% improvement in pp-PASI score from baseline between treatment groups.		
Key Secondary Objective			
Estimand Attribute	Definition		
Treatment	Deucravacitinib 6 mg QD versus Placebo		
Population	Participants with moderate-to-severe non-pustular palmoplantar psoriasis		
Variable	pp-PGA 0/1: Individual patient’s binary outcome (Yes or No) of achieving pp-PGA 0/1 at Week 16		
Intercurrent Events (ICEs)	Event	Strategy	Description
	Discontinuation of intervention and study early prior to Week 16 assessment	Composite variable	Participant will be counted as a non-responder
	Lost to follow-up prior to Week 16 or otherwise missed assessment at Week 16	Composite variable	Participant will be counted as a non-responder
Population-level Summary	Odds ratio of achieving pp-PGA 0/1 at Week 16 between treatment groups.		

Abbreviations: pp-PASI, palmoplantar Psoriasis Area and Severity Index; pp-PGA, palmoplantar Physician Global Assessment; QD, once daily.

Table 10.4.1-2: Summary of the Attributes of the Main Estimand for the Primary and Key Secondary Objectives of Genital Psoriasis Sub-protocol

Primary Objective			
Estimand Attribute	Definition		
Treatment	Deucravacitinib 6 mg QD versus Placebo		
Population	Participants with Moderate-to-severe genital psoriasis		
Variable	s-PGA-G 0/1: Individual patient’s binary outcome (Yes or No) of achieving s-PGA-G score of 0 or 1 at Week 16		
Intercurrent Events (ICEs)	Event	Strategy	Description
	Discontinuation of intervention and study early prior to Week 16 assessment	Composite variable	Participant will be counted as a non-responder
	Lost to follow-up prior to Week 16 or otherwise missed assessment at Week 16	Composite variable	Participant will be counted as a non-responder
Population-level Summary	Odds ratio of achieving s-PGA-G score of 0 or 1 at Week 16 between treatment groups.		
Key Secondary Objective			
Estimand Attribute	Definition		
Treatment	Deucravacitinib 6 mg QD versus Placebo		
Variable	Change from baseline GenPs itch numerical rating scale (NRS)		
Intercurrent Events (ICEs)	Event	Strategy	Description
	Discontinuation of intervention and study early prior to Week 16 assessment	Composite variable	Baseline Observation Carried Forward (BOCF) will be applied.
	Lost to follow-up prior to Week 16 or otherwise missed assessment at Week 16	Composite variable	Last Observation Carried Forward (LOCF) will be applied (including the baseline value if necessary).
Population-level Summary	Adjusted mean difference between treatment groups.		
Second Key Secondary Objective			
Estimand Attribute	Definition		
Treatment	Deucravacitinib 6 mg QD versus Placebo		
Variable	s-PGA 0/1: Proportion of participants achieving s-PGA score of 0 or 1 at Week 16		
Intercurrent Events (ICEs)	Event	Strategy	Description
	Discontinuation of intervention and study early prior to Week 16 assessment	Composite variable	Participant will be counted as a non-responder
	Lost to follow-up or otherwise missing	Composite variable	Participant will be counted as a non-responder

Table 10.4.1-2: Summary of the Attributes of the Main Estimand for the Primary and Key Secondary Objectives of Genital Psoriasis Sub-protocol

	endpoint data at or prior to Week 16 assessment		
Population-level Summary	Odds ratio of achieving s-PGA score of 0 or 1 at Week 16 between treatment groups.		

Abbreviations: QD, once daily; s-PGA, static Physician's Global Assessment; s-PGA-G, static Physician Global Assessment Genitals; NRS, Numerical Rating Scale.

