10 STATISTICAL CONSIDERATIONS

10.1 Statistical Hypotheses

For the non-pustular PP psoriasis sub-protocol, the primary hypothesis is that the odds of achieving pp-PASI-75 at Week 16 in participants receiving deucravacitinib 6 mg QD are improved compared to participants receiving placebo.

The null hypothesis to be tested for the primary endpoint is the following:

- The odds of achieving pp-PASI-75 at Week 16 in participants receiving deucravacitinib 6 mg QD are the same as participants receiving placebo.

The null hypothesis corresponding to the key secondary endpoint is:

- The odds of achieving pp-PGA 0/1 at Week 16 in participants receiving deucravacitinib 6 mg QD are the same as participants receiving placebo.

For the GenPs sub-protocol, the primary hypothesis is that the odds of achieving s-PGA-G 0/1 at Week 16 in participants receiving deucravacitinib 6 mg QD are improved compared to participants receiving placebo.

The null hypothesis to be tested for the primary endpoint is the following:

- The odds of achieving s-PGA-G 0/1 at Week 16 in participants receiving deucravacitinib 6 mg QD are the same as participants receiving placebo.

The null hypothesis corresponding to the key secondary endpoint is:

- The mean change from baseline in GenPs Itch NRS score at Week 16 in participants receiving deucravacitinib 6 mg QD is not different from participants receiving placebo.

The null hypothesis corresponding to the second key secondary endpoint is:

- The odds of achieving s-PGA 0/1 at Week 16 in participants receiving deucravacitinib 6 mg QD are the same as participants receiving placebo.

[figure not shown]
Multiplicity Adjustment

[figure not shown]
The statistical comparisons for the primary efficacy endpoint and the key secondary endpoint will be carried out in a hierarchical order for each sub-protocol. The hierarchical testing will preserve the overall Type I error at 0.05 for each sub-protocol.

[figure not shown]
The primary endpoint for each sub-protocol will be tested with a 2-sided Type 1 error (α) of 0.05, and if statistical significance is met for the primary endpoint, testing will proceed with the 2-sided α of 0.05 passed down to each respective key secondary endpoint.

If statistical significance is not met for the primary endpoint, then subsequent p-values will be considered descriptive for that sub-protocol.

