10.4.3 Secondary Endpoint(s)

Key Secondary Endpoints

Table 10.4.3-1: Key Secondary Endpoint for Palmoplantar Psoriasis Sub-protocol

Key Secondary Endpoint	Description of Analysis	Time Frame
pp-PGA 0/1 is defined as a proportion of participants achieving pp-PGA 0/1 at Week 16	The analysis model for pp-PGA 0/1 (responder/non-responder) at Week 16, will use [REDACTED] to compare the response rates of deucravacitinib 6 mg QD to placebo for the FAS population. The odds ratio (ratio of odds in deucravacitinib 6 mg QD to the odds in placebo group) and the corresponding 2-sided 95% confidence interval (CI) will be provided. Estimates of proportions and their 2-sided 95% CIs will be provided. The NRI method will be applied to the analysis of the binary secondary efficacy endpoint for participants who discontinue early or who have otherwise missing endpoint data at the specified timepoint.	Week 16

Abbreviations: [REDACTED]; FAS, full analysis set; pp-PGA, palmoplantar physician global assessment; QD, once daily.

Table 10.4.3-2: Key Secondary Endpoints for Genital Psoriasis Sub-protocol

Key Secondary Endpoint	Description of Analysis	Time Frame
Change from baseline in GenPs itch NRS score	The analysis model for the continuous secondary endpoint, change from baseline in GenPs itch NRS at Week 16, will use analysis of covariance (ANCOVA) with intervention [REDACTED]. The baseline value will be added into the model as a covariate. Intervention differences based on least-squares (LS) means and the corresponding 2-sided 95% CIs will be provided for the difference between deucravacitinib 6 mg QD and placebo. For the continuous secondary efficacy endpoint, multiple imputation will be used for missing data.	Week 16

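### The alpha-controlled genital itch NRS endpoint has two incompatible missing-data rules: BOCF/LOCF in the estimand table, multiple imputation in the analysis tables

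*Combined protocol and SAP*

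**What the plan says.** Three tables set the handling of missing Week 16 data for the change in GenPs itch NRS.

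- **Section 10.4.1, Table 10.4.1-2 (main estimand).** For discontinuation of intervention and study before Week 16: "Baseline Observation Carried Forward (BOCF) will be applied". For loss to follow-up or an otherwise missed Week 16 assessment: "Last Observation Carried Forward (LOCF) will be applied (including the baseline value if necessary". Both are called composite variable strategies. The summary measure is "Adjusted mean difference between treatment groups".
- **Section 10.3, Table 10.3-2 (analysis set, itch NRS row).** "Participants who discontinued prior to Week 16 will be imputed using multiple imputation in the analysis dataset".
- **Section 10.4.3, Table 10.4.3-2 (analysis).** The model "will use analysis of covariance (ANCOVA) with intervention" and baseline as covariate, with other terms blacked out. Then: "For the continuous secondary efficacy endpoint, multiple imputation will be used for missing data".

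The endpoint is inside the error-controlled family. Section 10.1 states "The hierarchical testing will preserve the overall Type I error at 0.05 for each sub-protocol", and that after a significant primary result "testing will proceed with the 2-sided α of 0.05 passed down to each respective key secondary endpoint". Itch NRS is listed first and s-PGA 0/1 is called the second key secondary. Section 10.4 leaves procedures for missing data to a SAP to be finalised before the Week 16 lock.

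**The concern.** The rules cannot all be followed. For a participant who discontinues before Week 16, BOCF fixes the change at zero, whereas ordinary multiple imputation draws a change predicted from other participants' data. For a participant who is lost or misses Week 16, LOCF inserts one earlier score and treats it as observed, whereas multiple imputation carries the uncertainty into the standard error. The estimate, its standard error and the p-value then depend on which table the programmer follows. If the key secondaries are tested in the listed order, the itch verdict also decides whether s-PGA 0/1 is formally tested.

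The strategy label is a second, smaller fault. A composite strategy makes the event part of the outcome definition. A missed visit is missing data, and carrying an earlier score forward does not turn it into an outcome.

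**Working it through.** **Step 1: the rules side by side.**

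| Event before or at Week 16 | Table 10.4.1-2 | Tables 10.3-2 and 10.4.3-2 |
|---|---|---|
| Discontinuation | BOCF (change = 0) | Multiple imputation (both tables) |
| Lost, or Week 16 missed | LOCF, or baseline | Multiple imputation (Table 10.4.3-2) |

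A split reading, with BOCF for the event and multiple imputation for the remaining gaps, fails on both rows. Table 10.3-2 gives multiple imputation to participants who discontinued, and the LOCF row already covers the remaining gaps. The blacked-out text in Table 10.4.3-2 follows the intervention term of the model; the missing-data sentence is intact.

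**Step 2: inputs for the size.** From the documents: 2:1 allocation, ANCOVA with intervention and baseline, two-sided 0.05. The public text gives no N, SD, effect or dropout for this endpoint, so there is no planned figure to reproduce. Assumed:

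- N 90 or 150; true difference 1.0 or 1.5 NRS points; placebo change −1.5; residual SD 2.5
- missing fraction d of 5%, 10% or 15% in both arms, or 10% active and 20% placebo, unrelated to outcome within arm
- 60% of the missing are discontinuations and 40% are lost or missed
- an interim score, available for 60% of participants, showing on average 75% of the Week 16 change (otherwise baseline is carried forward)
- multiple imputation under missing at random, 20 imputations, from treatment, baseline and the interim score where available

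**Step 3: expected shift by hand.** Under BOCF/LOCF an arm's mean change is multiplied by

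F(d) = (1 − d) + 0.6d × 0 + 0.4d × (0.6 × 0.75) = 1 − 0.82d.

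So F(5%) = 0.959, F(10%) = 0.918, F(15%) = 0.877 and F(20%) = 0.836. With equal dropout the difference shrinks by 4.1%, 8.2% or 12.3%.

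Unequal dropout, active −3.0 and placebo −1.5 (true difference −1.5):

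- 10% active, 20% placebo: 0.918 × (−3.0) − 0.836 × (−1.5) = −2.754 + 1.254 = −1.50, no shift
- 20% active, 10% placebo (not simulated): 0.836 × (−3.0) − 0.918 × (−1.5) = −2.508 + 1.377 = −1.13, a shift of about 25%

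**Step 4: simulation.** 400 trials in each of 16 scenarios, each trial analysed under both rules. Four of the scenarios:

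| N | True difference | Missing, active/placebo | BOCF/LOCF: estimate (SE), power | Multiple imputation: estimate (SE), power | Verdicts differ |
|---|---|---|---|---|---|
| 90 | 1.5 | 15%/15% | −1.34 (0.558), 65% | −1.52 (0.596), 72% | 12.8% |
| 150 | 1.0 | 15%/15% | −0.86 (0.426), 50% | −0.98 (0.460), 56% | 13.2% |
| 150 | 1.0 | 10%/20% | −1.01 (0.426), 65% | −0.97 (0.464), 55% | 13.0% |
| 150 | 1.5 | 5%/5% | −1.42 (0.434), 90% | −1.48 (0.443), 92% | 3.2% |

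Over all 16 scenarios:

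- With equal dropout the BOCF/LOCF estimate was about 4% to 13% nearer zero than multiple imputation, in line with step 3. With 10%/20% the mean estimates agreed within about 4%.
- The BOCF/LOCF standard error was smaller every time, by 2% to 8%.
- Verdicts differed in 3% to 13% of trials, in both directions: only BOCF/LOCF significant in about 1% to 12%, only multiple imputation in about 0.5% to 10%.

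The simulation error on a 13% rate is √(0.13 × 0.87/400) = 1.7 percentage points.

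**The case against.** - **The SAP will settle it.** Sections 10.4 and 10.4.1 have the SAP finalised before the Week 16 lock, and Section 7.3.1 unblinds the sponsor only at that lock. A reader might infer that the conflict lets the sponsor choose the rule after seeing the data. The documents do not support that: the stated process fixes the rule first. What stands is that the protocol contradicts itself, and that a SAP choosing one rule would still contradict at least one protocol table.
- **The form of multiple imputation is not stated.** The two tables do not say missing at random. Multiple imputation around a return-to-baseline value would keep the intent of BOCF for discontinuations. This stands, so the gaps above hold only for missing-at-random imputation. The LOCF row conflicts in either case.
- **A smaller standard error is not always an error.** A reader might infer that both single-imputation rules understate uncertainty. Under a true composite strategy, zero change is the defined outcome after discontinuation, not a guess. The charge fits LOCF only, and part of the 2% to 8% gap reflects a different estimand.
- **The endpoint is secondary.** It is formally tested only if the primary endpoint succeeds. True, but it then carries the full two-sided 0.05.

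**Conclusion.** The contradiction holds on the text alone and needs no assumption. For one error-controlled endpoint and the same participants, the protocol gives two rules, labels neither as sensitivity, and nothing in the supplied text chooses between them. The mislabelling of LOCF as a composite strategy also holds.

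The size is illustrative. Under the assumptions listed, the rules differ by several percent in estimate and standard error and reverse the significance verdict in roughly 3% to 13% of trials. The gap grows with the missing fraction and, as step 3 shows, depends on the balance of dropout between arms. A more lopsided assumption would give larger figures, but neither those nor the ones here are properties of this trial. It is a defect of specification to be corrected before the lock, not evidence of post-hoc selection.

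**What to change.** Before the Week 16 lock and unblinding, make Tables 10.3-2, 10.4.1-2 and 10.4.3-2 state one main rule for itch NRS.

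1. **Lost to follow-up or missed Week 16.** Replace LOCF with multiple imputation, which Table 10.4.3-2 already states. Give the model: within randomised arm, from baseline and double-blind visits only, with no open-label data after Week 16. Drop the composite label for this row.
2. **Discontinuation of intervention and study.** Keep that event wording. Shortening it to discontinuation of intervention could overwrite real data, because Sections 8.1 and 8.1.2 keep participants who stop treatment in follow-up. Use any observed Week 16 score. Otherwise name one strategy in all three tables: either the composite or return-to-baseline value, which keeps the intent of the main estimand table, or multiple imputation with a stated model.
3. **The other rule.** Keep it as a labelled sensitivity analysis.

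The cost is table and SAP wording plus one imputation program. The standard error will be slightly larger than under LOCF. If return-to-baseline is kept, the estimated effect will be smaller than under missing-at-random imputation when discontinuation is similar in the two arms or higher on active treatment. For example, with 9% discontinuing in each arm (60% of 15%) and a true difference of 1.5, the expected difference is 0.91 × 1.5 = 1.37.
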